Specific Aim 2: To determine the incidence of developing a septic arthritis in patients with a non-operatively treated traumatic arthrotomy.

Hypothesis 2: Non-operative treatment of small traumatic arthrotomies will have an extremely low rate (<10%) of subsequent septic arthritis over a 3-month period.

Specific Aim 3: To determine the incidence of developing a septic arthritis in patients with operative treatment of a traumatic arthrotomy.

Hypothesis 3: Operative treatment of traumatic arthrotomies will have an extremely low rate (<5%) of subsequent septic arthritis over a 3-month period.

Specific Aim 4: To determine the need for additional surgery (ex: foreign body removal) in patients with a non-operatively treated traumatic arthrotomy.

Hypothesis 4: Non-operative treatment of small traumatic arthrotomies will have an extremely low rate subsequent surgery over a 6-month period.

Specific Aim 5: To provide a description of traumatic arthrotomies successfully treated non-operatively.

Hypothesis 5: Arthrotomies will be less than 1 cm with a soft tissue injury amenable to closure in the ED. Arthrotomies will be more likely to be due to GSW's and scraping mechanisms rather than direct penetration.

Study Design

Prospective Multi-center Observational Cohort
Retrospective chart review

Study Population

Inclusion Criteria

1. Any patient 18 and older with a traumatic arthrotomy (of any major joint) confirmed by saline load test, direct visualization of a capsular rent or intra-articular contents, or air in the joint on CT or radiographs.
 - a. Major Joints Include:
 - i. Knee
 - ii. Elbow
 - iii. Wrist
 - iv. Shoulder
 - v. Hip
 - vi. Ankle

Exclusion Criteria

1. Patients who will have severe problems with maintaining follow-up

Method for Selecting Samples

Potential patients will be prospectively identified at the time of the initial consultation or at the first clinic follow-up appointment based on the diagnosis of a traumatic arthrotomy (Diagnostic criteria noted in inclusion criteria above).

Patients will be screened by their inclusion and exclusion criteria, and if met will be considered for enrollment in the study.

Retrospective chart review

The study will also conduct a retrospective chart review of patients who presented with a traumatic arthrotomy during the enrollment period, however were unable to be reached for consent after multiple attempts over a period of two years.

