Information about injury and treatment outcomes will be collected from the medical record.

Representativeness of the Sample

The study population will be representative of the typical trauma population.

Patients of all ages, genders, ethnicities, and backgrounds will be included in this study. Based on previous clinical series of patients at our institution, we expect that 70% of our patients will be men and 25% minority patients.

Definition of Variables

Outcome Variables

- Primary Outcomes
 - Cost of treatment
 - Adverse Events
 - Development of septic arthritis
 - Return to operating room for any reason (ie: foreign body removal)
 - Rehospitalization
 - Development of osteomyelitis
- Secondary Outcomes
 - Superficial wound infection
 - Extra-articular infection requiring a prolonged course of antibiotics or local wound care.
 - Pain 1 – 10 Scale
 - Current
 - Worst in last 24 hours
 - At rest
 - Bearing weight
 - Ambulating
 - Return to work or previous level of activity

Demographic Variables and Covariates

- Demographic Information

- Age
- Gender
- BMI
- Mechanism of injury
- Smoking Status
- Comorbidities
- Employment status
- Workers compensation status
- Additional Injuries
- Arthrotomy Characteristics
 - Mechanism of arthrotomy
 - Abrasion
 - Laceration
 - Puncture
 - GSW
 - Blast injury
 - Degree of contamination
 - Size of arthrotomy (mm)
 - Shape of arthrotomy
 - Method of Diagnosis
 - Visualization
 - Air on CT or radiograph
 - Saline load
- Treatment Characteristics
 - Antibiotics administered
 - Timing
 - Duration
 - Indication for Surgery
 - OR for additional injury
 - Intra-articular fracture requiring operative fixation
 - Heavily contaminated
 - Intra-articular loose body
 - Large arthrotomy
 - Intra-articular hardware

Potential Confounders

As a prospective observational study, the patient's treatment will not be altered by their inclusion in the study. No guidelines will be provided to influence the treating surgeons' decision making. All surgeons will have treated patients based on their own expert opinion and biases, which will undoubtedly differ between surgeons. The purpose of the study is to show that some traumatic arthrotomies can be treated non-operatively based on surgeon discretion, and having a variety of different arthrotomies will add to the descriptive nature of the study.

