At the initial consultation, patient demographic information, arthrotomy characteristics, treatment variables, and additional injuries will be obtained. At each follow-up appointments, pain level will be assessed by a member of the treatment team and recorded. Patient will complete the VR-12 to assess quality of health at 3 month after time of their injury. Patients may be followed prospectively for a total of one year after the time of their injury. Patients released from care prior to their one year appointment will be contacted via telephone by a member of the research staff to assess final outcomes. The total cost of care, including hospital and office charges, will be recorded at the one year mark. Patients still requiring care at the 3 month visit as a direct result of treatment of their traumatic arthrotomy will continue to be followed for a total of one year.

Follow-Up

A minimum necessary follow-up of 3 months or 1 year for patient requiring care as a direct result of treatment of their traumatic arthrotomy. Patients released from care after this time period without developing septic arthritis will be considered a successful therapy. If a patient is discharged from clinic prior to 3 months or 1 year, a member of the research team will contact the patient by telephone or by mail to obtain final follow up information.

Data Collection

All data will be entered into REDCap, a web-based data entry and management system that provides logic checks on input and checks for invalid entries. Data will be entered continuously as they are collected and stored in univariate form. We will also run standard checks for outliers, duplicates and other types of errors which may occur within a complex data file. All data files will be password protected and hard copies of blinded patient records will be maintained in locked cabinets in the research office.

Study Duration

Patients will continue to be enrolled for 2-years or until 25 patients are treated non-operatively, whichever comes first.

Statistical Analysis

Standard statistical tests will be used. Descriptive statistics including means and standard deviations, or counts and percentages will be reported. The principal analysis will compare cost of care using logistic regression. Also, demographic and baseline variables will be compared between operative and non-operative patients using t-test and chi-square test where applicable.

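### Patients unreachable for consent enter by chart review with record-only outcomes, and the plan has no rule for short charts or for combining them with the prospective cohort, so the 3-month septic arthritis rates depend on a choice not yet made

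*Combined protocol and SAP*

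**What the plan says.** Study Design lists a prospective multi-center cohort and a retrospective chart review. The chart review covers patients who presented during the enrollment period but were "unable to be reached for consent after multiple attempts over a period of two years". For them, "Information about injury and treatment outcomes will be collected from the medical record". No search of outside records or claims is described.

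The Follow-Up section states "A minimum necessary follow-up of 3 months or 1 year for patient requiring care" as a direct result of treatment. It then says "Patients released from care after this time period without developing septic arthritis will be considered a successful therapy". For a patient discharged from clinic early, "a member of the research team will contact the patient by telephone or by mail to obtain final follow up information". The section does not say whether any of this covers chart-review patients. Under Intervention, follow-up frequency and duration are left to the attending surgeon.

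The only exclusion criterion is "Patients who will have severe problems with maintaining follow-up".

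Hypothesis 2 claims an "extremely low rate (<10%) of subsequent septic arthritis over a 3-month period" after non-operative treatment. Hypothesis 3 claims an "extremely low rate (<5%) of subsequent septic arthritis over a 3-month period" after operative treatment. Study Duration ends enrollment at two years or at 25 non-operative patients. Statistical Analysis is a single section. It does not mention the chart-review group, missing outcomes or censoring.

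**The concern.** The chart-review patients are defined by failed contact, and contact is how the plan closes the gap when a patient leaves clinic early. A septic joint treated at another hospital need not appear in the index record, and nothing in the study ensures that the chart runs to 3 months. The plan also excludes patients expected to follow up poorly while admitting, by another route, patients who could not be reached. It does not comment on the tension.

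Hypotheses 2 and 3 are absolute thresholds on a safety outcome. A patient whose event is missed but who stays in the denominator pulls the rate toward the hypothesis. With few patients the margin is thin: in a non-operative group of 25, two events is 8% and three is 12%, so one unseen infection decides which side of 10% the point estimate falls. The sections on confounding discuss surgeon selection and observer effects, but not whether outcomes are ascertained equally in the two sources.

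**Working it through.** The documents give no figure on this point to reproduce, so the check is a sensitivity calculation.

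**Inputs from the protocol:** thresholds of 10% and 5% at 3 months (Hypotheses 2 and 3); 25 non-operative patients (Study Duration).

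**Assumed, because the protocol gives no values:** f, the share of the analysed group that comes from chart review; s, the share of that group's events visible in the record; and the retention shares in rule B. The true rate is taken as equal in both sources.

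**Rule A: pool the groups and read a chart that stops as no event.** Observed rate = true rate × [1 − f(1 − s)].

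| True rate | f | s | Observed rate |
|---|---|---|---|
| 12% | 0.4 | 0.5 | 12% × 0.80 = 9.6% |
| 12% | 0.2 | 0.5 | 12% × 0.90 = 10.8% |
| 10% | 0.1 | 0.5 | 10% × 0.95 = 9.5% |
| 10% | 0.3 | 0.5 | 10% × 0.85 = 8.5% |
| 10% | 0.5 | 0.25 | 10% × 0.625 = 6.25% |
| 5% | 0.1 | 0.5 | 5% × 0.95 = 4.75% |
| 5% | 0.3 | 0.5 | 5% × 0.85 = 4.25% |
| 5% | 0.5 | 0.25 | 5% × 0.625 = 3.1% |

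A true 12% falls below 10% only when f(1 − s) exceeds 1 − 10/12 = 0.167. The case f = 0.4, s = 0.5 gives 0.20 and crosses; f = 0.2, s = 0.5 gives 0.10 and does not. A true 15% would need f(1 − s) above 1 − 10/15 = 0.333; f = 0.4 with s = 0.25 gives 0.30, so it reads as 10.5% and does not cross.

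**Effect on the threshold.** Take 25 analysed non-operative patients and judge Hypothesis 2 on the point estimate, so that two or fewer recorded events falls below 10%. The binomial probability of that is 0.54 at a recorded rate of 10%, 0.64 at 8.5% and 0.75 at 7% (a true 10% with f = 0.4, s = 0.25: 10% × 0.70). For scale, even 0/25 has an exact two-sided 95% interval of 0 to 13.7%.

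**Rule B: pool the groups but drop chart-review patients without a 3-month record.** Let a be the share of cases kept and b the share of non-cases kept, with true rate p = 0.10 and f = 0.3.

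Observed rate = [(1 − f)p + f·p·a] / [(1 − f) + f(p·a + (1 − p)b)].

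- a = 0.9, b = 0.5: (0.07 + 0.027) / (0.70 + 0.162) = 0.097/0.862 = 11.25%.
- a = b = 0.5: (0.07 + 0.015) / (0.70 + 0.15) = 0.085/0.85 = 10.0%.
- a = 0.4, b = 0.6: (0.07 + 0.012) / (0.70 + 0.174) = 0.082/0.874 = 9.4%.

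Rule A can only lower the rate. Rule B can move it either way. The protocol chooses neither.

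**The case against.** A reader might infer that the plan sets no minimum follow-up for these patients, that infections treated elsewhere will count as non-events, and that the rates are therefore biased low. The documents do not support that much.

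- The 3-month minimum stands in a general Follow-Up section that is not limited to consented patients. Its application to the chart review is unstated rather than ruled out.
- Success is defined as release after the minimum period without septic arthritis. A chart ending sooner does not meet that definition, and nothing says it is to be read as event-free.
- Pooling is not stated. The chart review is listed as a separate design component.
- Failing to reach someone for research consent does not show that the patient missed clinic. Some of these charts may run well past 3 months.
- The exclusion criterion is a forward-looking judgement about follow-up, so admitting these patients is in tension with it but does not break it.

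A reader might also infer that missed charges favour non-operative care in the cost comparison. Data Collection records hospital and office charges at one year and names no source for outside bills for any patient, so the gap is not specific to the chart review. No figure shows loss to be larger in one treatment group.

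All of this stands, and it removes any claim of a certain direction. It does not remove the gap: outcomes come from the record alone, the contact safeguard cannot realistically cover these patients, and no rule handles short charts or the combination of the two sources.

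**Conclusion.** The concern holds in conditional form. If chart-review patients are pooled and a silent chart is read as no event, the Hypothesis 2 and 3 rates are understated by the factor 1 − f(1 − s). In the examples shown, a true 10% reads as 6.25% to 9.5%, and a true 12% can pass below the 10% threshold. If short charts are dropped, a true 10% reads as 9.4% to 11.25%. These figures illustrate size and rest on assumed shares and an equal true rate in both sources; the 25 is used only as an analysed group size, since the plan does not say whether chart-review patients count toward it. Because the result turns on a rule the plan does not contain, that rule could be chosen after the data are seen. On cost, missing outside charges may lower the recorded totals, but the direction of any bias in the operative versus non-operative difference is not established. The point should be addressed before analysis; confidence is medium.

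**What to change.** 1. Record the date of last documented contact for every chart-review patient.
2. Report the Hypothesis 2 and 3 rates separately for the prospective and chart-review groups. Take prospectively followed patients with confirmed 3-month status as the main estimate, and state how many prospective patients lack it.
3. In the chart-review group, do not read a chart ending before 3 months as event-free. Keep the patient, censor at last contact and report a Kaplan-Meier 3-month rate. Dropping short event-free charts while keeping charts with events would bias the rate upward.
4. Censoring assumes that loss is unrelated to outcome, which may fail in either direction. Add best-case and worst-case bounds, treating all unknown outcomes first as non-events and then as events.
5. Show the pooled rate, and the cost comparison with and without chart-review patients, as sensitivity analyses.
6. State that chart-review patients do not count toward the 25. Linking enrollment to informed consent may already imply this.

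The cost is protocol and analysis wording plus one form field. The price in the results is smaller denominators, wider intervals and a main estimate that represents hard-to-reach patients less well, although the protocol aims to represent the typical trauma population. Reporting the chart-review group alongside keeps that limitation visible.

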The observational nature of this study will introduce a selection bias based on the surgeon's comfort level of treating traumatic arthrotomies non-operatively. Larger and more heavily contaminated arthrotomies will be far more likely to be treated operatively compared to smaller, less contaminated arthrotomies. Any comparisons made between operative and non-operative treatment will have to be made between a matched cohort of arthrotomies of similar severity.

Although the treatment of patients should not be altered by their inclusion in the study, the possibility of a Hawthorne (observer) effect bias exists. The treating surgeon's decision making may potentially be altered by participation in this study.

Patient Safety

Patients involved in the study will not have their medical care altered in any way by their participation. A data safety monitor will be appointed to periodically assess for adverse events. .

Methods

Patient Identification and Enrollment

Patients will be identified at the time of the initial consultation or first clinic follow-up visit based on the presence of a traumatic arthrotomy, of any major joint, based on the criteria outlined above. Patients meeting the inclusion and exclusion criteria will be deemed eligible for the study. Eligible patients will be approached by a member of the treatment team to further discuss the study. If the patient agrees, a member of the research staff will discuss the study in greater detail and obtain informed consent.

Intervention

There will be no alterations in patient care by their inclusion in the study. The attending surgeon will determine the treatment plan, follow-up frequency, and follow-up duration. The need for additional surgery will also be determined by the attending surgeon. The development of septic arthritis or need to proceed to the operating room for foreign body removal will be deemed as adverse events and will be reported to the data safety monitor as they occur.

Data Collection

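### Pain has no fixed assessment time: it is recorded at appointments the surgeon schedules, and the protocol does not say whether the final telephone or mail contact collects it

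*Combined protocol and SAP*

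**What the plan says.** The combined protocol and SAP lists "Pain 1 – 10 Scale" among the secondary outcomes under Outcome Variables. It has five items: current pain, "Worst in last 24 hours", pain at rest, bearing weight and ambulating. No time point is attached.

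The only stated collection rule is in the first Data Collection section: "At each follow-up appointments, pain level will be assessed by a member of the treatment team and recorded". The Intervention section leaves those appointments to clinical judgement: "The attending surgeon will determine the treatment plan, follow-up frequency, and follow-up duration".

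One patient-reported measure does have a fixed time: "Patient will complete the VR-12 to assess quality of health at 3 month after time of their injury".

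Two sentences cover patients who leave care early. Data Collection says that those released before their one-year appointment "will be contacted via telephone by a member of the research staff to assess final outcomes". Follow-Up, for discharge earlier than its 3-month or 1-year minimum, says this: "a member of the research team will contact the patient by telephone or by mail to obtain final follow up information". Neither sentence lists what is asked.

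**The concern.** Pain after an injury normally changes with time, so a score means little without knowing when it was taken. Here the timing and number of scores follow from how care is going. A patient who does well may be released early and give few readings, all soon after injury. A patient with continuing problems may return for months and give many.

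A pain summary built from these readings would combine three things: the treatment, the time since injury, and who was still attending. If the summary were split by operative and non-operative care, part of any difference could come from the visit schedules. Even a single overall mean would have no clear time reference. A common-time score that was not collected cannot be recovered afterwards.

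**Working it through.** The plan gives no figure for pain to reproduce: no visit dates, standard deviation, effect size or power calculation. The check is a comparison of sections.

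1. **Starting point.** Data collected at entry are described thus: "At the initial consultation, patient demographic information, arthrotomy characteristics, treatment variables, and additional injuries will be obtained". Pain is not listed, so no baseline score is specified that could help to separate early differences from later ones.

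2. **During care.** Data Collection ties readings to appointments, and Intervention lets the surgeon set them. No target visit or window is given. Data Collection mentions a 3-month visit and a one-year appointment but attaches pain to neither. A patient who attends at 3 months would have pain recorded under the general rule. A patient released before then would not, unless the later contact asks for it.

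3. **After release.** The text allows two readings of the final contact.
   - *It does not ask about pain.* Patients released early then contribute scores only up to release.
   - *It does ask about pain.* Follow-Up sets the minimum at 3 months, or 1 year where care for the arthrotomy is still needed. The last score would then fall at a time that depends on recovery, and scores taken by clinic staff would be mixed with scores taken by telephone or mail.

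   On either reading, the protocol does not secure a score at one common time.

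4. **Link to treatment group.** Potential Confounders expects larger and dirtier wounds to go mainly to surgery, and expects surgeons to differ in their decisions. Schedules chosen by those surgeons for patients of differing severity cannot be assumed equal. The document gives no schedule by group, so a difference is plausible but not shown.

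5. **Planned safeguard.** Potential Confounders requires comparisons of operative and non-operative care to use arthrotomies matched on severity. Matching aligns the wounds, not the assessment times: two patients with similar wounds, one operated on and one not, can still be seen on different schedules.

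6. **Analysis.** Statistical Analysis names a cost comparison, baseline comparisons and regressions for predictors of poorer outcomes. It gives no pain time point, repeated-measures method or adjustment for time since injury.

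7. **Chart-review patients.** The Retrospective chart review section adds patients who could not be reached for consent and takes their outcomes from the medical record. Any pain scores they have depend on the care they received, and they cannot be asked at a fixed time.

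8. **Size.** To a first approximation, the timing part of a group difference is

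   timing difference ≈ (fall in pain per month) × (gap in mean assessment time, in months),

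   with a further part that depends on who is still attending. The documents give neither factor, nor the share released early, so no value can be computed.

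**The case against.** The strongest reply is that pain sits under Outcome Variables, so a call made to assess final outcomes would naturally include it. A reader might infer from the Data Collection rule that pain is recorded only in clinic, or that it is not asked at 3 months. The documents support neither. They are silent on the content of the final contact, and a patient attending at 3 months falls under the existing rule. The gap at 3 months is confined to patients released before then, and exists only if the contact omits pain. This part of the objection stands, and it limits how far readings can be said to come from patients still in care. It does not remove the problem, because the timing of that contact also depends on recovery.

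Second, no operative versus non-operative comparison of pain is named, and pain is in none of the five aims. That stands and keeps the point small. But descriptive statistics are promised, and the regressions for poorer outcomes do not say which outcomes they cover. A pain mean is hard to interpret in either use when assessment times vary.

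Third, matching on severity might narrow differences in follow-up that arise from severity. It may do so in part, but it does not set a common time.

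A reader might also infer that pain is in fact measured at different times in the two groups. That is a reasonable expectation, not something the documents state.

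**Conclusion.** The point holds as a low-priority improvement to a secondary outcome. Pain has no protocol-set time, its stated collection follows surgeon-determined appointments, and the content of the final contact is unspecified. Assessment times may therefore differ between operative and non-operative patients, and readings may over-represent those still in care. The cost, septic arthritis and reoperation aims do not use pain and are unaffected.

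The size is unknown. A reader might infer an artefact of 1 to 2 points on the 1–10 scale, by assuming that pain falls 0.5 to 1 point per month and that last scores come at about 1 month in one group and 3 months in the other (0.5 × 2 = 1; 1 × 2 = 2). Neither the rate nor the 2-month gap is in the documents, and with no gap the same formula gives 0. A last score at 1 month also assumes that the later contact omits pain. The figure should not be taken as a likely size.

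The conclusion rests on two assumptions: that pain changes with time after injury, and that visit schedules vary with recovery or severity.

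**What to change.** - For all consented prospective patients, collect the five pain items at 3 months after injury, alongside the VR-12. Do this at the visit, or by the planned telephone or mail contact if the patient has already been released. State the allowed window and record the mode of collection.
- Name 3-month pain as the analysed pain outcome.
- Report clinic-visit pain descriptively, with days since injury.
- Leave chart-review patients out of the 3-month pain analysis, or show them separately, since they have medical-record data only.

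This leaves the surgeon's visit schedule and all treatment decisions untouched. The cost is a short protocol addition and a slightly longer call or form. The drawback is that some scores will come by telephone or mail and not in clinic, so the mode should be reported with the results.

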Despite the relative dearth of evidence supporting the practice of formally irrigating and debriding all open joint injuries, significant healthcare expenditures and additional risks of general anesthesia are undertaken to address this problem. Although the administration of general anesthesia has become extremely safe, it still carries the risk of serious consequences such as heart attack, stroke, and even death (Lanier WL, *Am Surg*, 2006)(Botney R, *Int J Radiat Oncol Biol Phys*, 2008). Patients with multiple medical comorbidities are at an even greater risk of a serious perioperative complication (Wolters U, *Br J Anaesth*, 1996).

In addition to the risks of undergoing anesthesia, there are significant costs associated with any operation. A patient diagnosed with an isolated traumatic knee arthrotomy can expect to leave the hospital with a bill of at least \$15,000 based on conservative estimates provided by the Department of Research Finance at Carolinas Medical Center. In an era where healthcare costs are spiraling out of control, determining which interventions are efficacious will be paramount in shaping healthcare resource utilization and maintaining long-term sustainability.

Conclusion

To our knowledge, there is no evidence to support the practice of prophylactic irrigation and debridement of traumatic arthrotomies that would otherwise be amenable to treatment in the emergency department. It is the opinion of the senior authors of this study, who are both experienced orthopaedic traumatologists at high-volume level 1 trauma centers, that small, mildly contaminated traumatic arthrotomies could be treated with antibiotics and close follow-up alone, if they are amenable to closure in the emergency department. Instead of a hospital admission and operative procedure, these patients could be safely discharged from the emergency department with local wound care and antibiotics alone resulting in significant healthcare savings and minimizing the risks of undergoing general anesthesia and a surgical procedure.

Research Plan

Specific Aim 1: To compare the cost of medical care in patients with traumatic arthrotomies treated with surgical irrigation and debridement versus non-operative treatment with local wound care.

Hypothesis 1: Patients with traumatic arthrotomies will have an average hospital bill of \$15,000 less than those treated with surgery.

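### Pain is assessed by the unblinded treatment team on items not tied to the injured joint, so pain from other injuries, probably more common after surgery, can enter any group comparison

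*Combined protocol and SAP*

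**What the plan says.** Pain is a secondary outcome. Under Outcome Variables it appears as "Pain 1 – 10 Scale" with five items: pain now, "Worst in last 24 hours", at rest, when weight-bearing and when walking. No item names a joint or body region, and the list does not say who gives the number.

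Under Methods, Data Collection, at each follow-up visit "pain level will be assessed by a member of the treatment team and recorded". The next sentence treats the quality-of-health measure differently: "Patient will complete the VR-12 to assess quality of health at 3 month after time of their injury". Patients released from care early are contacted by research staff, by telephone under Data Collection and by telephone or mail under Follow-Up.

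The Intervention section says "The attending surgeon will determine the treatment plan, follow-up frequency, and follow-up duration". No blinded or independent pain assessor is described.

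The only exclusion criterion concerns follow-up, so patients with other injuries may enter. Additional injuries are listed among the covariates and collected at the initial consultation. The indications for surgery include "OR for additional injury". Potential Confounders requires operative versus non-operative comparisons to use a cohort matched on arthrotomy severity. Statistical Analysis specifies an adjusted treatment comparison for cost only.

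**The concern.** Two features of the pain measurement could separate the groups for reasons unrelated to how the arthrotomy was treated.

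- **Other injuries.** A patient with another painful injury may report that pain on an item that names no joint. Because surgery for another injury is itself a route into the operative group, such patients are likely to be over-represented there. To that extent the error makes non-operative care look less painful.
- **Assessor.** The person collecting pain belongs to the team giving care and knows the treatment. The protocol says of surgeons: "All surgeons will have treated patients based on their own expert opinion and biases, which will undoubtedly differ between surgeons". The background conclusion gives the senior authors' own view that "small, mildly contaminated traumatic arthrotomies could be treated with antibiotics and close follow-up alone". An unblinded assessor with a prior view can influence how a question is asked or an answer recorded.

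At stake is whether an observed pain difference, or the lack of one, can be attributed to treatment of the arthrotomy. The aims on cost, septic arthritis and further surgery are not affected.

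**Working it through.** The documents give no SD, effect size, power or sample size for pain, so there is no planned figure to reproduce. The check has two parts.

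**1. Does anything in the plan remove other-injury pain from the pain outcome?**

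- Eligibility: no, other injuries are not excluded.
- Item wording: none is given that restricts the answer to the injured joint. The weight-bearing and walking items also do not isolate an elbow, wrist or shoulder, all of which are eligible joints.
- Matching: it covers arthrotomy severity. Two small, clean wounds match whether or not one patient went to the operating room for an injury elsewhere.
- Adjustment: the specified treatment model has cost as its outcome. The further regressions on predictors of poorer outcome name neither pain nor additional injuries.
- Data: additional injuries are recorded, so adjustment is possible but not planned.

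**2. How large could the shift be?**

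From the protocol (Study Duration): enrolment stops at 25 non-operative patients or 2 years, so n = 25 at most. Everything else is assumed: pain SD 2.5 points; 25 to 75 operative patients; another painful injury in 40% of operative and 10% of non-operative patients; 2 to 3 points added by such an injury; no true difference in the injured joint.

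Shift in the group difference = (difference in share) × (points added):

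- (0.40 − 0.10) × 2 = 0.6 points
- (0.40 − 0.10) × 3 = 0.9 points

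The right yardstick is the standard error of the difference, SE = SD × √(1/25 + 1/n_op):

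- 25 v 25: 2.5 × √(0.04 + 0.04) = 0.71
- 25 v 75: 2.5 × √(0.04 + 0.0133) = 0.58

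Shift divided by SE:

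| | 25 v 25 | 25 v 75 |
|---|---|---|
| 0.6 points | 0.85 | 1.04 |
| 0.9 points | 1.27 | 1.56 |

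If a two-sided 5% normal test of pain were run, its false-positive rate would be 1 − Φ(1.96 − shift/SE) + Φ(−1.96 − shift/SE). That is about 14% at 0.85 SE and about 34% at 1.56 SE.

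Over a wider assumed range (imbalance of 10 to 50 percentage points, 1 to 2 points added), the shift runs from 0.1 to 1.0 point and the false-positive rate from about 5% to 41%. With no imbalance and no assessor effect it stays at 5%.

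A differential assessor effect of 0.5 point, also assumed, would alone give about 11% (25 v 25) to 14% (25 v 75). The documents give no basis for its direction or size.

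**The case against.** The strongest reply is that the protocol says little about pain and the concern fills the gaps.

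- A reader might infer that the team scores the patient's pain. The text says assessed and recorded. On a numeric scale that includes worst pain over the past day, the natural reading is that staff ask and the patient answers. This stands. It reduces assessor influence without removing it.
- A reader might infer that the assessor is the person who chose the treatment. The attending surgeon chooses treatment, while any member of the team may assess pain. They may differ.
- A reader might infer that treater expectation favours non-operative care. The documents do not support a direction: the quoted opinion is the senior authors', the study is multi-center, and the protocol says that surgeons' biases differ.
- A reader might infer that the form asks about pain in general. The documents hold a variable list, not the form. What can be said is that the plan does not tie the items to the injured joint.
- Surgery for another injury is one of six listed indications, with no frequency given, and other injuries not needing surgery can occur in either group. The imbalance is therefore likely, but its size is unknown.
- Pain appears in no aim or hypothesis and has no named treatment-group test. This stands and limits the importance of the point.

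The other-injury route survives all of this, because it operates whoever gives the number.

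**Conclusion.** The point holds as a minor one about a secondary outcome. Nothing in the plan keeps pain from other injuries out of a pain comparison, and the listed indications make such injuries likely to be more common in the operative group. Under the assumed 30-point imbalance the bias is comparable to sampling error. It is not always larger: a 0.6-point shift is below the SE of 0.71 with 25 patients per group. Setting the shift against the SE of the non-operative mean alone, 2.5/√25 = 0.5, would make it look larger than sampling error throughout, but that is the wrong comparison for a group difference. The figures show scale only, since every input except the 25 is assumed.

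Unblinded assessment adds a risk of unknown direction and size.

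**What to change.** For prospectively enrolled patients:

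1. Have the patient complete the pain items, as already planned for the VR-12, before seeing the surgeon.
2. Word each item as pain in the injured joint.
3. Use the same wording when research staff collect final outcomes by telephone or mail, so that a change of assessor and mode does not also change the question.
4. State that any operative versus non-operative pain comparison will be reported by, or adjusted for, the additional injuries already recorded.

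The cost is a reworded one-page form, one sentence in the analysis section and some incomplete forms. No extra staff, visits or patients are needed. Two limits remain: patients in the retrospective chart review cannot use the form, and joint-specific wording does not separate arthrotomy pain from that of a fracture in the same joint, which is another listed indication for surgery.
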